## List of Abbreviations

AE	Adverse Event/Adverse Experience
CFR	Code of Federal Regulations
CRF	Case Report Form
DSMB	Data and Safety Monitoring Board
ECM	Extracellular Matrix
ECG	Electrocardiogram
FDA	Food and Drug Administration
GCP	Good Clinical Practice
HIPAA	Health Insurance Portability and Accountability Act
IB	Investigator's Brochure
IDS	Investigational Drug Services
IND	Investigational New Drug Application
IRB	Institutional Review Board
LSR	Local Skin Reaction
PCCA PP	Professional Compounding Centers of America Pracasil™-Plus
PHI	Protected Health Information
PI	Principal Investigator
RCT	Randomized Clinical Trial
SAE	Serious Adverse Event/Serious Adverse Experience
SOP	Standard Operating Procedure
SPP1	Osteopontin
SSE	Surgical Scar Excision
TP	Topical Pentamidine + PCCA Pracasil™-Plus
US	Ultrasound
VAS	Visual Analog Scale
VSS	Vancouver Scar Scale
POSAS	Patient and Observer Scar Assessment Scale

**Study Summary**

Title	Double Blind, Single-Center, Randomized, Within-Subject Placebo, Phase I Study Evaluating the Effects of Topical Pentamidine in Prevention of Hypertrophic Scar Formation
Running Title	Novel Topical Gel for Hypertrophic Scar Prevention
IRB Protocol Number	17-005230
Phase	Pilot Study
Methodology	Double Blind, Single-Center, Randomized, Within-Subject Placebo Phase I Study
Overall Study Duration	3 months
Subject Participation Duration	3 months
Single or Multi-Site	Single site
Objectives	Evaluate safety of topical pentamidine (TP) as an adjuvant to surgical scar excision (SSE) in the treatment of hypertrophic scar formation. Safety will be measured by serial monitoring for adverse events following the procedure and during treatment duration. Secondarily, study will evaluate drug quality and standardizations as well as investigate initial signs of efficacy.
Number of Subjects	10
Diagnosis and Main Inclusion Criteria	Hypertrophic scar diagnosed in Mayo Clinic Department of Dermatology or Division of Plastic Surgery, Rochester, Minnesota.
Study Product, Dose, Route, Regimen	Pentamidine, delivered as topical formulation containing 2% TP in silicone-containing base, PCCA Pracasil™-Plus (PP), versus placebo base alone. Approximately 1.8 mL of product in allotted single dose containers will be applied every 48 hours for 4 weeks following surgical scar excision.
Duration of Administration	Once every 48 hours for 4 weeks.
Reference therapy	SSE with silicone compounding base only (PCCA PP).
Statistical Methodology	The primary analysis will use descriptive statistics to document adverse events between treated and untreated lesions. The secondary analysis will use paired t-test or Wilcoxon signed rank test to compare the change in lesion height and characteristics between the treated and placebo groups following SSE (TP + PCCA PP vs. PCCA PP alone). In addition, two-factor analysis of variance (ANOVA) with repeated measures on both factors will be used to evaluate the effect of treatment and follow-up time for other continuous measures such as Vancouver Scar Scale (VSS) and Patient and Observer Scar Assessment Scale (POSAS).

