in PCCA PP or PCCA PP. Topical agent B will treat the distal portion of the scar and contain either TP in PCCA PP or PCCA PP alone. 1-2cm in the middle of the scar will remain untreated as the border zone. It is known that blood perfusion influences scar formation; thus to reduce potential bias from distal scar site receiving reduced blood flow compared to proximal scar site, treatment application will be randomized to scar site. Prior to treatment initiation, patients will undergo scar excision procedure with a 24-hour recovery period. Treatments will be provided in single dose containers for application every 48 hours following surgical recovery (total of 14-16 applications; total treatment duration of 4 weeks).

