### 3.5 Secondary Study Endpoints

**Aim #2:** Evaluate initial signals of efficacy as measured by US dimensions (length, width and height) and volume quantification, skin biopsy histological features (semi-quantitative assessment of skin fibrosis) and patient-reported outcome metrics (per VSS and POSAS). Preoperative US as well as 2 week and 4 week postoperative US will be compared based on formal quantification of the hypertrophic scar lesion volume size (unit of measure: cm^3). Preoperative 5-mm skin biopsy and 4 week postoperative skin biopsy will be used for histological evaluation (including epidermal hyperplasia/hyperkeratoses, hair follicles, apocrine glands, smooth muscles, fibroplasia, vascular proliferation and collagen orientation) [27] and epidermal scar thickness calculation. Quality of life and scar elevation scores will also be assessed at serial follow-up as measured by VSS and POSAS.

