## 4 Subject Selection Enrollment and Withdrawal

### 4.1 Inclusion Criteria

- Males and females 18 years of age or older.
- Diagnosis of hypertrophic scar by a Mayo Clinic plastic surgeon or dermatologist
- Target disease or condition: Hypertrophic scar
- Subject with a hypertrophic scar that meet all of the following criteria:
  - Linear scar  $\geq 3$  cm to  $\leq 40$  cm in length
  - Present for minimum 6 months
  - Located anywhere in the body except on the face or front of neck
  - Resulting from surgical or traumatic injury, or other scar considered appropriate for surgical excision
- Ability to safely undergo scar excision surgery
- Capacity to provide informed consent
- Ability to comply with protocol
- Subject is judged, by the clinical investigator, to be healthy as evidenced by lack of clinically significant abnormal findings on medical history, physical examination, electrocardiogram, vital signs, and clinical laboratory tests.

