## 5.2 Treatment Regimen

First dose will be applied 24 hours post-surgical scar excision, then scheduled every 48 hours. Approximately 1.8 mL (0.06 oz) of topical pentamidine (TP) or PCCA PP control will be topically applied via single dose containers provided the day of surgery and at their 2-week postoperative follow-up visit. Participants will receive two sets of single dose containers (set A and set B). One set will be randomized to contain TP with de-identified label; the other set will be randomized to contain PCCA PP with de-identified label. Each set (A and B) will contain 8 single dose containers, all with a de-identified label. The study drug will be applied every 48 hours. Specifically, topical agent (either TP or PCCA PP) will be applied to either the distal or the proximal end of the wound. Study participants will receive treatment application education during their pre-operative visit; further details provided in Section 6.1. Treatment duration is 4 weeks.

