#### **5.5 Packaging**

The research pharmacy will order 300 mg Pentam vials via Rochester Methodist Campus (RMC) pharmacy purchasing specialists from APP Pharmaceuticals. Pentam vials will be stored within the research pharmacy (20-25°C) and sent to the compounding pharmacy when the study drug order is placed. The study drug order will be initiated by the study coordinator following patient consent, and as needed based on the date of surgery and 2 week postoperative visit. The Principle Investigator will sign the order which is then forwarded to the research pharmacy to be filled. For production, 300 mg Pentam (pentamidine isethionate) product will be compounded into non-aqueous silicone base vehicle (Pracasil™-Plus (PCCA #30-4655; PCCA PP) for 2% topical gel.

The compounding pharmacy will prepare the single containers for storage and dispensation by the research pharmacy. The research pharmacy will dispense a specified quantity of containers according to patient-specific prescription signed by IRB-authorized prescriber. The study coordinator will pick up the prescription from the research pharmacy and provide to the patient on visit 2 (day of surgery) and visit 3 (2 week postop clinic visit). Each dispensation will contain 8 active and 8 placebo containers to be applied every 48 hours; all containers (used and unused) will be returned by the patient at their next follow-up visits.

The research pharmacy will perform randomization schema to determine treatment to dispense for proximal versus distal scar areas. The research pharmacy maintains electronic records of investigational medication inventory and dispensation activities for the study; thus randomization will be performed for enrolled patients electronically via Medidata and Scientific Data Management System (SDMS). All Mayo Clinic Research Pharmacy staff members are required by policy to complete the Mayo Clinic Human Subject Protection and CITI Good Clinical Practice Training once every 3 years. The designated Research Pharmacy staff member assigned primary responsibilities for the study reviews all sponsor documents and prepares instruction sheets outlining storage, handling, electronic order entry and preparation of all investigational agents as indicated in the study protocol and pharmacy manual.

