### 6.2 Visit 1 (Preoperative period)

Patients will receive a comprehensive pre-operative evaluation. This evaluation will gather information relating to medical history as well as include a standard clinical exam and necessary laboratory studies. Once consent is provided and patient meets inclusion criteria as a qualified participant for the study, photographs will be taken of the lesion area with a digital camera and/or photography service. Pre-operative ultrasound and/or 3D imaging will also be performed to determine initial scar height and morphology. The scar will be assessed using the Vancouver Scar Scale (VSS) [28] and the Patient and Observer Scar Assessment Scale (POSAS) [29]. These scales will determine the initial level of hypertrophy and scar attributes before treatment initiation. Safety evaluation will include assessment of systemic and local safety and thus baseline clinical exam with neuropsychiatric evaluation, laboratory studies (including hepatic and renal function, complete blood count with differential, blood glucose level and calcium) and baseline cardiac monitoring with electrocardiogram (ECG) will be performed.

This visit will include two 5-mm skin punch biopsy (one from distal site and one from proximal scar site) performed under local anesthesia in a dedicated procedure room. Alternatively, the first punch biopsy may occur prior to the surgical procedure while under anesthesia. This sample will be processed by the study staff for histological/molecular evaluation to analyze scar characteristics.

Patients will also be educated on proper treatment application. Treatment regimen and duration will be summarized. For example, following their surgical scar excision procedure, they will be provided single dose containers with topical study agents. There will be two different formulations given to patients; one is the placebo control (PCCA PP) and the other is the active treatment (TP). Patients and providers blinded to treatment regions but their treatment label will have appropriate instructions for application either at the distal or proximal region.

Based on the distal or proximal region assigned to each formulation by the pharmacist and appropriately labeled single dose containers, patients will apply the unit dose. Compound A (either TP or PCCA PP) will be applied to proximal site and Compound B (either TP or PCCA PP) will be applied to the distal site; 1-2 cm border zone in the middle of the scar will remain untreated.

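### Treatment is randomised to scar end because the ends may heal differently, but no balanced allocation is stated and the efficacy test leaves scar end out: a minor loss of precision, not bias

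*Combined protocol and SAP*

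**What the plan says.** Section 3.1 states that perfusion influences scar formation and gives the reason for randomising treatment to scar end: "to reduce potential bias from distal scar site receiving reduced blood flow compared to proximal scar site".

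The allocation is described in two places. Section 5.2 says of the two container sets: "One set will be randomized to contain TP with de-identified label". Section 5.5 says: "The research pharmacy will perform randomization schema to determine treatment to dispense for proximal versus distal scar areas", and adds that this is done electronically. Section 5.7.3 leaves the assignment with the research pharmacist. None of these sections gives a ratio, a block size or a 5:5 constraint.

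The efficacy analysis is in the Study Summary: "The secondary analysis will use paired t-test or Wilcoxon signed rank test to compare the change in lesion height and characteristics". A two-factor ANOVA for other continuous measures such as VSS and POSAS has treatment and follow-up time as its factors. Section 7.2 names only a paired t-test, for a primary hypothesis that it does not spell out. Scar end appears in none of these analyses.

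On the reference for change, section 3.5 says: "Preoperative US as well as 2 week and 4 week postoperative US will be compared". Section 6.2 says: "Pre-operative ultrasound and/or 3D imaging will also be performed to determine initial scar height and morphology". That imaging precedes surgery; section 3.1 says: "Prior to treatment initiation, patients will undergo scar excision procedure with a 24-hour recovery period".

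**The concern.** The protocol itself names scar end as a likely cause of different outcomes within a patient. When a design factor is expected to affect the outcome, the usual practice is to balance it and to put it in the analysis. Here the plan does neither explicitly.

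Two things can follow. First, a consistent difference between ends goes into the error term of the paired test and lowers its power. Second, if allocation happens to be uneven, part of the end difference is carried into the treatment estimate for that particular trial. With at most 10 pairs (section 3.2), analysis of completers only (section 7.3) and limited replacement of withdrawals (section 4.4.1), there is little room for either. What is at stake is modest: efficacy is a secondary aim (section 2), looking for early signals.

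**Working it through.** **The plan's own power figure.** Section 7.1 claims 80% power for 1.3 SD with a two-sided unpaired t-test at 5%. Taking 10 per group (an assumption from the 10 subjects), the noncentrality is 1.3 × √(10/2) = 2.91 on 18 df, and power is 78.5%. The figure therefore reproduces approximately, but for an unpaired test. It says nothing about the paired analysis or about scar end, so a separate model is needed.

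**Model.** For patient i, let D_i be the pentamidine-minus-base difference: D_i = τ + δ·s_i + e_i. Here s_i = +1 if pentamidine is proximal and −1 if distal, δ is the proximal-minus-distal difference without any drug effect, and e_i has SD 1. From the documents: 10 pairs, two-sided 5%. Assumed, because the documents give no values: τ and δ. Results are from 200,000 simulated trials per setting.

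**Power at 5:5.** The plain paired t-test uses 9 df. Its error variance is inflated on average to 1 + (10/9)δ², for example 1.28 at δ = 0.5. The model with the scar-end term uses 8 df and noncentrality τ√10, free of δ.

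| End effect δ (SD) | τ = 1: plain / with term | τ = 1.3: plain / with term |
|---|---|---|
| 0 | 80% / 79% | 95% / 95% |
| 0.25 | 78% / 79% | 95% / 95% |
| 0.5 | 72% / 79% | 92% / 95% |
| 1.0 | 48% / 79% | 77% / 95% |

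The τ = 1.3 column reads the plan's 1.3 SD as SDs of the within-patient difference, which is itself an assumption.

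**Balance.** If allocation were a simple coin toss (not stated), the Binomial(10, 0.5) probabilities are 25% for 5:5, 41% for 6:4, 23% for 7:3 and 11% for 8:2 or worse. With k proximal pentamidine allocations, the plain mean difference is shifted by δ(2k − 10)/10: zero at 5:5, ±0.4δ at 7:3, ±0.6δ at 8:2. Type I error of the plain test, given the split:

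| Split | δ = 0.5 | δ = 1.0 |
|---|---|---|
| 5:5 | 3% | 0.7% |
| 6:4 | 3.7% | 1.7% |
| 7:3 | 6% | 6% |
| 8:2 | 10.5% | 20% |

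Averaged over all splits it is 5.0% to 5.2%. With the term it is 5% at every split, but at τ = 1 its power falls from 79% at 5:5 to 77% at 6:4, 72% at 7:3 and 60% at 8:2.

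**When the gain disappears.** Suppose end effects vary between patients with the same overall size (root mean square 0.5 SD). Plain versus adjusted power at τ = 1 is then 72% v 79% if fully consistent, 71% v 72% if the mean is 0.25 SD, and 71% v 70% if the mean is zero. If the outcome is change from the pre-operative value, only the part of the end effect not already present before surgery remains in D_i. Take a correlation of 0.5 between the pre- and post-operative between-end differences, with equal SDs. The change then has variance 1 + 1 − 2(0.5) = 1. If a 1.0 SD end effect was half present before surgery, 0.5 SD remains and power is 72% plain v 79% with the term. If it was fully present, nothing remains and power is 80% v 79%.

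**The case against.** The strongest reply is that a paired t-test or signed rank test under randomised sides is standard and valid, and that this is a 10-patient safety pilot in which no decision is stated to hang on the efficacy p-value. That stands, and it is why the point is minor. It is also fair that the end-effect sizes are assumed, that the loss at 0.5 SD shrinks from 7 points to 3 if the true effect is 1.3 SD rather than 1 SD, and that the 48% and 72% figures apply only to an end effect that is consistent and survives in the analysed difference.

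Four stronger readings are tempting, and the documents do not support them.

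- **The treatment comparison is biased.** It is not: randomising the ends protects the test over all allocations. The inflated error rates are conditional on a lopsided split.
- **Allocation is by simple randomisation.** The documents give no method, so a balanced list may already exist.
- **Change has no stated baseline.** Sections 3.5 and 6.2 give a pre-operative reference. What is missing is narrower: the Study Summary and section 7 do not define the subtraction or the time point, and the reference describes the scar that is later excised.
- **The pre-operative value should not be subtracted.** Whether subtraction helps depends on the correlation between pre- and post-operative between-end differences and on the ratio of their SDs. It helps only when the correlation exceeds half the pre/post SD ratio. The documents give neither quantity.

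Scars may also lie off the limbs ("Located anywhere in the body except on the face or front of neck"), where proximal and distal are less obvious. That does not undermine randomised labels. It is missing detail, and it makes a consistent end effect somewhat less likely.

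**Conclusion.** The point holds as a minor one. The plan gives a reason to expect the scar ends to differ, states no balanced allocation, and omits scar end from every efficacy test it names. The consequence is lost precision and exposure to chance imbalance in a secondary analysis.

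At 5:5 with a 1 SD effect, the plain test loses from nothing to about 30 points of power against the adjusted one as the end effect rises from 0 to 1.0 SD. At 1.3 SD the largest loss in that range is about 18 points. These sizes rest on assumed end effects that are consistent across patients and not subtracted out. Otherwise the gain is about a point or slightly negative. The case for change rests less on a large expected gain than on its low price.

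**What to change.** 1. In section 5.5, state that the research pharmacy uses a blocked list with pentamidine proximal in five patients and distal in five, and that a replacement subject takes the allocation of the subject replaced. With two withdrawals and one replacement under section 4.4.1, inheriting the allocation always leaves 5:4. Drawing it by coin toss leaves 6:3 in 22% of cases.
2. In the Study Summary and section 7.2, specify that the within-patient pentamidine-minus-base difference is regressed on a ±1 scar-end term, with the intercept as the treatment effect. The same model serves whether the outcome is the post-operative value or the change. The text should say which of these it is and at which time point.

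Cost: wording and a list, with no new data, since each patient's allocation is already recorded. With no end effect, the term takes power from 80% to 79% at 5:5, and from 75% to 73% with nine pairs split 5:4. It costs more when allocation is uneven (72% power at 7:3, 60% at 8:2). Balance without the term leaves the test conservative when an end effect exists. The list and the term should therefore be adopted together.

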## 1 Introduction

This document is a protocol for a human research study. This study will be carried out in accordance with applicable United States government regulations and Mayo Clinic research policies and procedures.

### 1.1 Background

Hypertrophic scars are formed by an excessive tissue response to dermal injury characterized by local fibroblast proliferation and overproduction of collagen [1, 2]. With an incidence of hypertrophic scarring occurring at rates of 40-70% post-surgery and up to 91% following burn injury [3, 4], an effective topical treatment would offer immense benefits to a patient's quality of life. Current treatments for hypertrophic scars rely on management via surgical intervention [5], compression therapy [6], silicone gel sheeting [7], laser [8, 9] or corticosteroid injection [10, 11]. While these may offer temporary relief, interventions such as corticosteroid therapy have recurrence rate of up to 50% after 5 years [12, 13] and various skin complications including dermal atrophy, skin ulceration and hypo/hyperpigmentation [14].

The use of silicone gel sheeting to prevent and treat hypertrophic scarring is still relatively new, and started in 1981 with treatment of burn scars [15]. Topical silicone gel sheet and silicone cream have been evaluated as efficacious in treating keloids and hypertrophic scars due to their hydrating effect on the stratum corneum [16-18]. Silicone-based therapies are currently being investigated in several clinical trials for hypertrophic abdominal scar (NCT01078428), hypertrophic and keloid scar (NCT00754247), and post-surgical hypertrophic scarring (NCT01861119; NCT00849004) (<http://clinicaltrials.gov/>) [19]. Preliminary results from the Investigation of a Novel Silicone Dressing to Maximize the Outcomes of Scar Revision Procedures (IMPROVE) trial (NCT01430130) showed improvement in the visual analog scale (VAS) in the silicone dressing cohort. This proof-of-concept demonstration suggests that silicone-based therapy may provide a solution for hypertrophic scar prevention. Despite these findings, treatment of hypertrophic scarring varies and management targeting the root cause of abnormal wound healing is warranted.

Early inflammation following dermal injury is essential in the progression of normal wound healing; in contrast, chronic or excessive inflammation leads to pathological scarring and fibrosis [20, 21]. Our recent preliminary findings show that osteopontin (SPP1), a secreted chemokine-like protein [22] involved in intracellular signaling [23], modulates extracellular matrix (ECM) remodeling [24]; this interaction plays a role in scar formation as SPP1 is known to drive tissue fibrosis and aging [25]. Previous studies have shown that SPP1 local knockdown leads to accelerated repair and decreased granulation tissue and scar formation [26]. Thus, SPP1 expressed by wound fibroblasts as a consequence of signals from inflammatory cells may hinder the rate of wound repair and regeneration. Screening pharmaceutically active compounds that inhibit the SPP1 promoter led to the discovery of pentamidine isethionate, which inhibited SPP1 promoter activity by  $\geq 80\%$  with minimal in vitro cell toxicity.

Here we investigate a novel topical agent, SPP1 inhibitor, pentamidine isethionate, compounded in silicone-containing base, as an adjuvant therapy to surgical scar excision (SSE) to prevent adverse scarring and enhance skin rejuvenation by upregulating anti-fibrotic and anti-aging processes. Initial studies in rabbit ear hypertrophic scar formation model (n=18 rabbits) showed significantly reduced scar elevation index following 4 weeks of topical pentamidine (TP) treatment

compared to silicone base, PCCA Pracasil™-Plus (PP), versus no treatment. As such, TP serves as a primed agent for trial as a clinical-grade product for human use.

